The anticipated study duration per participant without a recurrence while on therapy is maximum of approximately 24 weeks (ie, approximately 1 day for screening + maximum 12 weeks of treatment for the presenting episode + 12 weeks of follow-up). Participants will have daily assessments during hospitalization and weekly visits for assessments during ongoing treatment with caplacizumab and IST. There will be 3 outpatient visits for assessments during the follow-up period. There will be two additional follow-up visits for participants who do not have ADAMTS13 activity levels of $\geq 50\%$ at the time of caplacizumab discontinuation.

Number of participants:

Approximately 61 participants will be enrolled in the study.

Intervention groups and duration:

All participants will receive open label caplacizumab daily until sustained ADAMTS13 activity normalization ($\geq 50\%$) is achieved at 2 consecutive visits, after platelet count normalization (defined as $\geq 150 \times 10^9/L \times 2$ consecutive values). The maximum duration allowed for caplacizumab treatment is 12 weeks for the presenting episode.

Study intervention(s)

This open-label single-arm study will be comprised of caplacizumab and IST without first-line TPE.

Investigational medicinal product (IMP): caplacizumab

- Formulation: lyophilized powder for solution for injection.
- Route(s) of administration: intravenous (IV) (for the first dose), subcutaneous (SC) (all subsequent doses).
- Dose regimen: Caplacizumab 10 mg (11 mg in US and Canada) IV for a single dose followed by caplacizumab 10 mg (11 mg in US and Canada) SC 4-6 hours after the IV dose (Day 1). An exception to this is detailed in [Section 1.3.4](#) footnote^a. This will be followed by caplacizumab 10 mg (11 mg in US and Canada) SC daily starting on Day 2 for a maximum treatment duration of 12 weeks for the presenting episode.

Note: Please see [Section 4.1](#) for additional details related to IMP administration.

Noninvestigational medicinal products(s) (NIMP)

Immunosuppressive therapy:

- Corticosteroids:
 - Formulation: Prednisone or Prednisolone,
 - Route(s) of administration: IV or oral,
 - Dose regimen: Prednisone or Prednisolone 1.0-1.5 mg/kg/day for 1 week and taper over 3 to 4 weeks based on institutional guidelines. The dose and duration of therapy may be adjusted as clinically indicated.
- Anti-CD20 antibody therapy:
 - Formulation: anti-CD20 antibody therapy (rituximab or biosimilar),

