The current standard of care for iTTP consist of a combination of TPE, IST and anti-vWF therapy (cicapacizumab) (4, 14). These treatments focus on the three major pathophysiological mechanisms in iTTP:

1. Therapeutic plasma exchange (TPE):

TPE, a procedure in which blood of the patient is passed through a medical device which separates out plasma from other components of blood and the patient's plasma is removed and replaced with a replacement solution such as colloid solution (eg, albumin and/or plasma) or a combination of crystalloid/colloid solution (15). Therapeutic plasma exchange replenishes the ADAMTS13 enzyme and removes anti-ADAMTS13 antibodies, and ULvWF multimers gradually from the circulation.

TPE is administered daily for the time needed to restore platelet counts to normal levels, which may take several days to weeks. Although the introduction of TPE treatment has substantially reduced mortality from around 90% to lower than 20%, in spite of greater

understanding of disease pathogenesis and the use of newer immunosuppressants, the mortality rate has not been further decreased until the availability of caplacizumab (12, 16, 17, 15, 18, 19, 20).

TPE is frequently associated with procedure and plasma-related complications. Reducing the duration of TPE, or eliminating TPE altogether, when possible, would therefore reduce the risk of patients experiencing these complications.

Complications of TPE

Although the introduction of TPE treatment has substantially reduced overall iTTP mortality from around 90% to lower than 20%, this therapeutic approach carries substantial morbidity and mortality risk in critically ill iTTP patients. Therapeutic plasma exchange related complications include procedural complications such as invasive catheter placement and associated AEs such as bleeding, thrombosis, infections, pneumothorax and plasma-related complications such as allergic reactions including anaphylaxis and serum sickness. Allergic reactions are more frequent due to large volumes of plasma required for the procedure. Fibrinogen levels may decrease after serial TPE procedures with cryoprecipitate depleted plasma as replacement (15).

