Study participants will not receive TPE as first-line therapy. However, participants may receive TPE if it is determined that there is lack of adequate response to treatment after first 24 hours or if there is any clinical deterioration at any time during the study, including during the first 24 hours (please see below for additional details). It is expected that the participant is hospitalized when the treatment is started, and the duration of initial hospitalization may vary based on clinical condition of the individual participant.

Caplacizumab treatment will be continued until sustained ADAMTS13 activity level of $\geq 50\%$ at 2 consecutive visits after platelet count normalization (defined as $\geq 150 \times 10^9/L \times 2$ consecutive values) or 12 weeks, whichever occurs first. Thus, the maximum treatment duration of caplacizumab will be 12 weeks for the presenting episode.

The post-treatment follow-up period will be 12 weeks. The anticipated study duration per participant without a recurrence while on therapy is maximum of approximately 24 weeks (ie, approximately 1 day for screening + maximum 12 weeks of treatment for the presenting episode + 12 weeks of follow-up).

Initial treatment regimen during hospitalization:

1. anti-vWF therapy: Caplacizumab

Recommended dose: Caplacizumab 10 mg (11 mg in US and Canada; see [Section 2](#)) intravenous (IV) for a single dose followed by caplacizumab 10 mg (11 mg in US and Canada) subcutaneous (SC) 4-6 hours after the IV dose (Day 1) (exceptions to this are detailed in [Section 1.3.4](#)). This will be followed by caplacizumab 10 mg (11 mg in US and Canada) SC daily starting on Day 2 for a maximum treatment duration of 12 weeks.

Note: The baseline ADAMTS13 activity level results from the local laboratory, available within 48 hours will be used to confirm the diagnosis of iTTP. It is expected that there will be minimal discrepancy between local and central laboratory ADAMTS13 activity levels. The central laboratory test results will be available only after 3-4 days.

- If the baseline central laboratory ADAMTS13 activity is <10% of normal → continue caplacizumab and IST.
- If the baseline central laboratory ADAMTS13 activity is between 10% - 20% of normal → use clinical judgment in deciding to continue or stop caplacizumab treatment after evaluation of the totality of signs and symptoms plus other laboratory data.

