- If there is persistent thrombocytopenia, defined as lack of a sustained platelet count increment or platelet counts of $<50 \times 10^9/L$ and a persistently raised LDH level ($>1.5 \times$ upper limit of normal [ULN]) despite five days of treatment.
- If there is clinical evidence of new or progressive ischemic organ injury (worsening of presenting signs and symptoms or appearance of new signs and symptoms such as but not limited to neurologic manifestations [seizures, sudden onset numbness or weakness of the face, arm, or leg especially on one side of the body, mental status changes including confusion, trouble speaking, or understanding speech, sudden visual impairment, sudden difficulty walking, loss of balance or coordination, sudden severe headache with no known cause], cardiac manifestations such as chest pain with or without electrocardiogram (ECG) changes suggestive of myocardial ischemia, increasing troponin, renal manifestations such as worsening serum creatinine at any time after starting therapy, TPE may be started at Investigator discretion at any point during the study, including the first 24 hours and cplacizumab and IST continued.

If participant needs TPE:

Recommend TPE with plasma (eg, fresh frozen plasma, solvent detergent/viral-inactivated plasma, cryosupernatant) at 1 to $1.5 \times$ estimated plasma volume. TPE should be performed daily according to standard site practice and continued at least for 2 days after the platelet count normalization ($\geq 150 \times 10^9/L$). Of note, TPE with 1 to $1.5 \times$ estimated plasma volume may be spread over multiple sessions within 24 hours. Tapering of TPE after platelet count normalization, defined as reducing its frequency to less than once per day, is strongly discouraged and if considered, should be discussed with the Medical Monitor.

Treatment plan for continued therapy with cplacizumab and IST regardless of hospitalization status:

If there is response to initial therapy:

- The participant will continue cplacizumab 10 mg (11 mg in US and Canada) SC daily until sustained ADAMTS13 normalization ($\geq 50\%$) at 2 consecutive visits after platelet count normalization defined as $\geq 150 \times 10^9/L$, or for 12 weeks, whichever occurs first. The maximum treatment duration of cplacizumab is 12 weeks for the presenting episode.

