- Immunosuppressive therapy will be continued as described earlier. If there is inadequate response to the initial immunosuppressive regimen (corticosteroids with or without anti-CD20 antibody therapy) and the ADAMTS13 activity level is <10% after 4 weeks of therapy, the Investigator may consider optimizing immunosuppression further (including adding anti-CD20 antibody if not done before) or consider alternative immunosuppressive therapies as per local standard of care.
- Laboratory monitoring of platelets and LDH will be performed weekly during the out-patient treatment phase and at the 3 follow-up visits*.
*Note: there will be two additional follow-up visits for participants who do not have ADAMTS13 activity levels of $\geq 50\%$ at the time of caplacizumab discontinuation.
- ADAMTS13 activity levels will be obtained once a week starting on Day 8 of caplacizumab treatment. If the ADAMTS13 activity level is <10% after 4 weeks of therapy, consider optimizing immunosuppression further.

If participant requires TPE:

- The participant will continue caplacizumab 10 mg (11 mg in US and Canada) SC daily until sustained ADAMTS13 normalization ($\geq 50\%$) at 2 consecutive visits after stop of daily TPE. During the time, the participant is receiving TPE, caplacizumab will be given after the TPE. The maximum treatment duration of caplacizumab is 12 weeks for the presenting episode.
- Immunosuppressive therapy will be continued as described earlier. If there is inadequate response to the initial immunosuppressive regimen (corticosteroids with or without anti-CD20 antibody therapy) and the ADAMTS13 activity level is <10% after 4 weeks of therapy, the Investigator may consider optimizing immunosuppression further (including adding anti-CD20 antibody if not done before) or consider alternative immunosuppressive therapies as per local standard of care.
- Laboratory monitoring of platelets and LDH will be performed weekly during the out-patient treatment phase and at the 3 follow-up visits*.
*Note: there will be two additional follow-up visits for participants who do not have ADAMTS13 activity levels of $\geq 50\%$ at the time of caplacizumab discontinuation.
- ADAMTS13 activity levels will be obtained once a week starting on Day 8 of caplacizumab treatment. If the ADAMTS13 activity level is <10% after 4 weeks of therapy, consider optimizing IST further.

Follow-up after treatment completion:

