1 INTRODUCTION

1.1 STUDY DESIGN

This is an open-label, single-arm, Phase 3, multicenter study to evaluate the efficacy and safety of caplacizumab and immunosuppressive therapy (IST) without first-line therapeutic plasma exchange (TPE) in adults with immune-mediated thrombotic thrombocytopenic purpura (iTTP).

The anticipated study duration per participant, without a recurrence while on therapy, is a maximum of approximately 24 weeks (ie, approximately 1 day for screening + maximum 12 weeks of treatment for the presenting episode + 12 weeks of follow-up). All participants will receive open-label caplacizumab daily until sustained disintegrin and metalloproteinase with a thrombospondin type 1 motif13 (ADAMTS13) activity normalization ($\geq 50\%$) is achieved at 2 consecutive visits, after platelet count normalization (defined as $\geq 150 \times 10^9/L$ for 2 consecutive values) or 12 weeks of caplacizumab treatment, whichever occurs first.

For participants who experienced a first clinical recurrence (exacerbation or relapse) during the overall study period, the ongoing treatment plan may be adjusted including a start or re-start of TPE and adjustment of IST regimen and caplacizumab therapy. In case that caplacizumab treatment is maintained for a first clinical recurrence, the visit schedule will be the same as during the initial treatment period.

[figure not shown]
The primary analysis will be conducted after study completion of all participants, ie, when all the participants will have discontinued from the study.

In addition, an interim analysis (IA) will be conducted after the first 30 participants with baseline ADAMTS13 activity of $<10\%$ have completed the study (eg ended treatment period per protocol and completed the follow-up period of 12 weeks) (see [Section 3.8](#) for further details). A Data Monitoring Committee (DMC), independent from the Sponsor, will be appointed to monitor the safety and the scientific integrity of this study on an on-going basis, and to provide in a timely fashion appropriate recommendations to the Sponsor.

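### For participants who receive TPE, the documents give two starting points for the ADAMTS13 rule that ends caplacizumab, and no passage says which one governs

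*Protocol*

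**What the plan says.** Most statements of the stopping rule count from platelet normalization:

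- **Protocol 1.1 Synopsis** (intervention groups and duration): "All participants will receive open label caplacizumab daily until sustained ADAMTS13 activity normalization" of at least 50% "is achieved at 2 consecutive visits, after platelet count normalization". It has no TPE exception.
- **Protocol 4.1, general text:** the two values are required "at 2 consecutive visits after platelet count normalization", or treatment ends at 12 weeks. Again there is no TPE exception.
- **Protocol 4.2:** the same starting point, stated for all participants.
- **SAP 1.1:** "All participants will receive open-label caplacizumab daily until sustained disintegrin and metalloproteinase" activity has normalized at two consecutive visits after platelet normalization, or 12 weeks. This is the only version in the SAP.

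One statement counts differently. The branch of **Protocol 4.1** for participants who require TPE continues caplacizumab until ADAMTS13 is at least 50% "at 2 consecutive visits after stop of daily TPE" and does not mention platelets.

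The same section says TPE should be daily and "continued at least for 2 days after the platelet count normalization". It also sets the sampling: "ADAMTS13 activity levels will be obtained once a week starting on Day 8 of caplacizumab treatment".

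**The concern.** For a participant on TPE, platelet normalization and the stop of daily TPE are different days if the TPE guidance is followed. An ADAMTS13 value drawn between them counts toward stopping caplacizumab under four passages and does not count under the fifth. That interval matters because, in the protocol's own background section, "Therapeutic plasma exchange replenishes the ADAMTS13 enzyme". A value of at least 50% drawn then may partly reflect donor plasma.

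The plan already separates the two events elsewhere. For participants requiring TPE, remission is assessed from the end of TPE (Protocol 4.2 and 9.2.2, SAP 3.2.1). Under the general wording, one of the two values that end treatment could therefore predate the start of remission assessment.

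Two things are at stake. Sites may stop the drug at different times, which carries through to exposure and to the secondary windows that run from the last dose. In addition, SAP 5.2 counts participants who completed treatment as per protocol, and SAP 3.8 uses the same idea to trigger the interim analysis. SAP 5.2 names a form field for study completion but none for treatment completion, so the governing rule needs to be clear.

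**Working it through.** The plan states no figure for this point, so the check compares the passages and applies both rules to the visit schedule.

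**1. Order of the two starting points.** Let N be the day platelets normalize and S the day daily TPE stops. Protocol 4.1 recommends S ≥ N + 2. Any two visits after S are then also after N, so a participant who meets the TPE-branch rule also meets the general rule. The TPE-branch date is the same or later.

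**2. When the dates differ.** Both rules need two consecutive values of at least 50%. They give different dates only if (a) such a value falls after N and by S, and (b) the next value is also at least 50%.

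**3. Example on nominal weekly days (8, 15, 22, ...).** Take N = 6, S = 9 and values of at least 50% on Days 8, 15 and 22.

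- General rule: Days 8 and 15 qualify, so treatment ends on Day 15.
- TPE branch: Days 15 and 22 qualify, so treatment ends on Day 22.

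If 50% is first reached after TPE has stopped (for example on Day 36), both rules give Day 43.

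**4. Sensitivity to the gap g = S − N.** Assumptions: N from Day 3 to Day 30 (28 cases), activity of at least 50% at every visit from N onward, nominal visit days, and only visits later than the starting day counted. For g up to 7, the number of cases with a weekly visit inside the gap is 28 × g/7 = 4g.

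| g (days) | Cases with different dates | Nominal shift |
|---|---|---|
| 2 | 8 of 28 | 7 days |
| 3 | 12 of 28 | 7 days |
| 5 | 20 of 28 | 7 days |
| 7 | 28 of 28 | 7 days |
| 10 | 28 of 28 | 7 days in 16, 14 days in 12 |

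These fractions are conditional on sustained activity from normalization onward, so they are not forecasts. The documents give no distribution of N, S or ADAMTS13 recovery for participants who start TPE in this trial.

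**5. Real spacing.** Weekly visits carry a window of ±3 days (Protocol 1.3.3). Two successive visits can therefore be 7 − 6 = 1 to 7 + 6 = 13 days apart, and the 12-week cap can shorten the shift. About one weekly visit or more is as precise as the size can be stated.

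**6. How many participants.** Protocol 9.4 and SAP 4 assume that 18% require TPE: 0.18 × 55 = 9.9, about 10 participants in the mITT population. That is the ceiling at the planned rate. The number who also meet (a) and (b) is unknown and may be 0.

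**The case against.** The strongest reply is that there is no conflict, only a general rule and a specific one. The treatment plan in Protocol 4.1 has two labelled branches, one for response to initial therapy and one for TPE. The anti-CD20 instruction uses the same pair of starting points, and the synopsis refers the reader to Section 4.1 for details of IMP administration. This is a plausible reading, but it is an inference. Three passages speak of all participants, no passage says the TPE branch prevails, and the synopsis pointer leads to a section that holds both rules.

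A second reply is that the dates may rarely differ. Other cohorts described in Protocol 2.3.2 had about 5 days of TPE and median platelet recovery of about 2.7 to 3.0 days on caplacizumab. If normalization fell on Days 3 to 5 with 2 further days of TPE, exchange would end on Days 5 to 7, before the nominal first draw on Day 8. Participants who start TPE here after an inadequate response may recover later, so this limits the likely size without removing the inconsistency.

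Three stronger readings are tempting and are not supported:

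- **A reader might infer that the analysis periods become ambiguous.** They do not. Protocol 9.2.1 and SAP 3.1 define the on-treatment and treatment-emergent periods by the actual last administration, and follow-up visits are dated from the actual last dose.
- **A reader might infer that any value in the gap delays stopping by a fixed 7 days or more.** The next value must also be at least 50%, and the visit window and the 12-week cap both alter the shift.
- **A reader might infer that the rules also conflict in the other direction, if TPE stops before platelets normalize.** That path departs from the TPE guidance in Section 4.1, and no passage describes it.

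Nor do the documents allow any difference in recurrence or bleeding risk to be quantified.

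**Conclusion.** The inconsistency is real and minor. For TPE participants the current text contains two starting points for the same stopping rule. They cannot coincide if the TPE guidance is followed, and the SAP reproduces only one of them. The effect is limited to the TPE path, at most about 10 of 55 participants at the planned rate, and only to those with two consecutive values of at least 50% of which the first falls between normalization and the stop of TPE.

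The primary responder count is unaffected, because a participant who required TPE is a non-responder whichever date applies. The interim analysis has no stopping rule and is not meant to change study conduct (SAP 3.8). What remains is variation between sites in when the drug is stopped, its downstream effect on exposure and secondary windows, and an unclear basis for counting per-protocol treatment completion. This conclusion rests on daily TPE continuing at least 2 days after normalization, as recommended. It takes no position on which starting point is clinically right.

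**What to change.** Reconcile the synopsis, the general text of Protocol 4.1, Protocol 4.2 and SAP 1.1 with the TPE branch of Protocol 4.1. For participants who receive TPE, state one starting event for the two ADAMTS13 visits, and say whether a platelet condition also applies (and, if so, whether it means one value or two consecutive values). Add a cross-reference to that rule wherever the text speaks of all participants. The branch for participants who respond to initial therapy needs no change.

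In the SAP, add one sentence saying that per-protocol treatment completion, in the disposition table (5.2) and in the interim trigger (1.1 and 3.8), is judged against that rule. The sponsor's clinical team decides which rule applies.

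The cost is a short protocol clarification and one SAP sentence. No new data or visits are needed.

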4.2 SCIENTIFIC RATIONALE FOR STUDY DESIGN

Caplacizumab is a Nanobody compound developed for the treatment of iTTP, a life-threatening thrombotic microangiopathy. It binds to the A1 domain of vWF and specifically inhibits the interaction between vWF and platelets, thereby immediately preventing the platelet adhesion and microthrombi formation responsible for the clinical consequences of the disease. The mechanism of action and safety profile of caplacizumab are both well documented at this time. Results of the HERCULES study, a double-blind, placebo-controlled Phase 3 study demonstrated that those treated with caplacizumab had better clinical outcomes, including faster normalization of the platelet count, and a lower incidence of a composite of iTTP-related death, recurrence of iTTP, or a major thromboembolic event during the treatment period as well as a lower rate of recurrence of iTTP during the trial than with placebo ([23](#)). In addition, published real-world evidence also demonstrate that caplacizumab with TPE and immunosuppression with corticosteroids and rituximab prevents unfavorable outcomes of the disease and substantially alleviates the burden of care in these patients ([24](#)). Current standard of care of iTTP includes caplacizumab, IST and TPE, but TPE is associated with many complications and increased morbidity ([15, 21, 22](#)). This open-label single-arm study is intended to establish efficacy of caplacizumab without first line TPE, while conferring a better safety profile by definition.

Based on the pathophysiology of iTTP and mechanism of action of caplacizumab, it is hypothesized that caplacizumab and IST without initial TPE, may be safe and effective as first line therapy for iTTP. This concept is supported by pre-clinical data as well as emerging real-world evidence ([2, 25, 26](#)). Another important consideration is the low incidence of iTTP, which has been reported to range from 3.1 to 6.0 cases per million ([6, 7, 30](#)). A fully powered 2-arm

study against a comparator, requiring a large sample size, would be challenging due to likely recruitment difficulties in this rare disease context. Therefore, a single-arm, open-label Phase 3, multicenter study to evaluate the efficacy and safety of caplacizumab and immunosuppression without first-line TPE in adults with an acute episode of iTTP will be conducted.

Adult participants with a clinical diagnosis of iTTP and a French TMA score of 1 or 2 will be enrolled. After confirmation of eligibility, participants will receive initial treatment consisting of caplacizumab and IST (corticosteroids \pm anti-CD20 antibody [rituximab or biosimilar]) without first-line TPE. However, participants may receive TPE if it is determined that there is lack of adequate response to treatment after first 24 hours or if there is any clinical deterioration at any time during the study including during the first 24 hours (see [Section 4.1](#) for details). All participants will receive open label caplacizumab daily until sustained ADAMTS13 activity normalization ($\geq 50\%$) is achieved at 2 consecutive visits, after platelet count normalization. The maximum duration allowed for caplacizumab treatment is 12 weeks and the post-treatment follow-up period will be 12 weeks for the presenting episode.

This study incorporates the revised consensus outcome definitions for iTTP published by the International Working Group for TTP that reflect current iTTP management (3) The primary endpoint, and many of the secondary endpoints of this study, are aligned with the consensus report. The primary endpoint is the proportion of participants achieving remission without requiring TPE during the overall study period. Remission is defined as sustained Clinical Response with either (a) no TPE and no anti-VWF therapy for ≥ 30 days (Clinical Remission) or (b) with attainment of ADAMTS13 activity level $\geq 50\%$ (Complete ADAMTS13 Remission), whichever occurs first. Remission is assessed starting from the clinical response (for participants not requiring TPE) or the end of TPE (for participants requiring TPE), until the end of study.

